### **Safety Objective**

The safety objective for this study is to evaluate the safety and tolerability of ocrelizumab 600 mg IV given every 24 weeks on the basis of the following endpoints:

- Rate and nature of adverse events
- Changes in vital signs, physical and neurological examinations, clinical laboratory results, locally reviewed MRI for safety (non-MS central nervous system [CNS] pathology) and concomitant medications (including pre-medications and medications used during and following ocrelizumab administration).

### **Exploratory Objectives**

The exploratory efficacy objective for this study is to further assess the efficacy of ocrelizumab 600 mg IV given every 24 weeks by monitoring patient-reported outcomes (PROs) related to quality of life (QoL), treatment satisfaction and other endpoints and analyses as follows:

- Multiple Sclerosis Impact Scale (MSIS)-29 (MS-specific QoL questionnaire)
- Treatment satisfaction questionnaire for medication (TSQM II)
- Patient reported outcome: SymptoMScreen
- MRI and clinical outcomes at 6 months and 1 year
- Predictors of NEDA and association between NEDA and disability or other efficacy parameters
- Severity of relapses (hospitalization for MS relapse, use of corticosteroids, residual disability)
- Employment status (WPAI)

- Proportion of patients who have no evidence of disease activity (NEDA, as per protocol defined events) during a 96-week period and starting from baseline.

## **Study Design**

### **Description of Study**

This study is a prospective, multicenter, open-label, efficacy, and safety study in patients with RRMS who have a suboptimal response to an adequate course of a DMT. An adequate course of prior DMT is defined as a stable dose of the same DMT administered for at least 6 months. The first dose of ocrelizumab will be administered as an initial dose of two 300-mg infusions (600 mg total) in 250 mL 0.9% sodium chloride each separated by 14 days (i.e., Days 1 and 15) followed by one 600-mg infusion in 500 mL 0.9% sodium chloride every 24 weeks for the study duration.

Patients will be assessed for efficacy and safety every 24 weeks. The study will consist of the following periods:

- Screening period: Up to 4 weeks
- Treatment period: Open-label treatment period of 96 weeks (last dose administered at Week 72)
- A follow-up period of at least 2 years, which is independent of the DMT administered

Follow-up Period: Patients who discontinue treatment early will be followed up for at least 96 weeks after the Early Treatment Discontinuation Visit. Patients who complete the 96 weeks Treatment Period and, in agreement with their treating neurologist, decide not to continue in a separate long-term extension (LTE) study, will be followed up for at least 96 weeks after the end of the Treatment Period. Patients who decide to leave the study and switch to commercially marketed Ocrelizumab, either after completion of the 96 weeks Treatment Period or after early discontinuation of the 96 weeks Treatment Period, will not enter the safety Follow-up Period.

Patients whose B-cells have not been repleted after 96 weeks of Follow-up Period will continue with visits every 24 weeks, and telephone contacts every 8 weeks, until B-cell repletion (Prolonged B-cell monitoring). If the patients are receiving other B-cell targeted therapies, then the Follow-up Period will be stopped at 96 weeks regardless of their B-cell count.

A structured telephone interview will be conducted by site personnel every 8 weeks between the study visits during the treatment period and follow-up to identify and collect information on any changes in the patient's health status that warrant an unscheduled visit (including new or worsening neurological symptoms) and possible events or infections.

### **Number of Patients**

This study will enroll 750 patients with RRMS who have had a suboptimal response to an adequate course of a DMT.

### **Target Population**

#### Inclusion Criteria

Patients must meet the following criteria for study entry:

- Signed informed consent form
- Able to comply with the study protocol, in the investigator's judgment
- Age 18 – 55 years, inclusive
- Have a definite diagnosis of RRMS, confirmed as per the revised McDonald 2010 criteria (Polman et al. 2011)

### **Ocrelizumab—F. Hoffmann-La Roche Ltd**

19/Protocol MA30005, Version 5

- Have a length of disease duration, from first symptom, of < 10 years. If the date of first symptom is unknown, then the diagnosis of RRMS should be of  $\leq 5$  years
- Have received no more than two prior DMTs, and the discontinuation of the most recent DMT was due to lack of efficacy
- Suboptimal disease control while on a DMT; a suboptimal response is defined by having at least one of the following events while being on a stable dose of the same DMT for at least 6 months:
  - One or more clinically reported relapse(s)
  - OR one or more T1 Gd-enhanced lesion(s)
  - OR two or more new and/or enlarging T2 lesions on MRI

In addition, in patients receiving stable doses of the same approved DMT for more than a year, at least one of the above events must have occurred within the last 12 months of treatment with this DMT.

- EDSS of 0.0 to 4.0, inclusive, at screening
- For women of childbearing potential: agreement to use an acceptable birth control method during the treatment period and for at least 6 months after the last dose of study drug.

A woman is considered to be of childbearing potential if she is postmenarcheal, has not reached a postmenopausal state ( $\geq 12$  continuous months of amenorrhea with no identified cause other than menopause), and has not undergone surgical sterilization (removal of ovaries and/or uterus).

The following are acceptable contraceptive methods: progestogen-only oral hormonal contraception, where inhibition of ovulation is not the primary mode of action, male or female condom with or without spermicide, and cap, diaphragm, or sponge with spermicide. A combination of male condom with cap, diaphragm, or sponge with spermicide (double-barrier methods) is considered acceptable

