#### Exclusions Related to Medications\*

- Receipt of a live vaccine or attenuated live vaccine within 6 weeks prior to the baseline visit. In rare cases when patient requires vaccination with a live vaccine, the screening period may be extended but cannot exceed 8 weeks
- Treatment with any investigational agent within 24 weeks of screening (Visit 1) or five half-lives of the investigational drug (whichever is longer) or treatment with any experimental procedures for MS (e.g., treatment for chronic cerebrospinal venous insufficiency)
- Contraindications to or intolerance of oral or IV corticosteroids, according to the country label, including:
  - a) Psychosis not yet controlled by a treatment;
  - b) Hypersensitivity to any of the constituents
- Previous treatment with B-cell targeted therapies (i.e., rituximab, ocrelizumab, atacicept, belimumab, or ofatumumab)
- Systemic corticosteroid therapy within 4 weeks prior to screening
- Any previous treatment with alemtuzumab (Campath/Mabcampath/Lemtrada), cladribine, mitoxantrone, daclizumab, laquinimod, total body irradiation, or bone marrow transplantation.
- Treatment with cyclophosphamide, azathioprine, mycophenolate mofetil, cyclosporine or methotrexate
- Previous treatment with natalizumab unless natalizumab was discontinued because of persistent anti-natalizumab antibodies
- Treatment with IV immunoglobulin (Ig) within 12 weeks prior to baseline

- Any previous treatment with an investigational MS DMT not yet approved at time of screening.
- History of recurrent aspiration pneumonia requiring antibiotic therapy
- Patients previously treated with teriflunomide, unless an accelerated elimination procedure is implemented before screening visit

Accelerated elimination procedure after stopping treatment with teriflunomide:

- cholestyramine 8g is administered 3 times daily for a period of 11 days, or cholestyramine 4g three times a day can be used, if cholestyramine 8g three times a day is not well tolerated,
- alternatively, 50g of activated powdered charcoal is administered every 12 hours for a period of 11 days

In cases where no pregnancy is expected teriflunomide plasma concentrations of 0.03-0.04 mg/ml are accepted to include the patient in study.

- Previous treatment with fingolimod or dimethyl fumarate if at baseline the lymphocyte count is below lower limit of normal (LLN). The provisions for stopping therapy as described in the respective SmPCs should be followed.

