Screening Disease History– Relapse

- Number of relapses in the last year as continuous and in categories (0, 1, 2, 3, ≥ 4) and (≤ 1 and >1)
- Duration since last onset of MS relapse prior to enrollment and its category (≤ 3 months, >3 and ≤ 6 months, >6 months)
 $(\text{date of baseline visit} - \text{date of last onset of MS relapse prior to enrollment} + 1) / 30.4375$
- Sites and symptoms for the most recent relapse

Note that for this analysis, if the date of the relapse is completely missing or if only the year is available, this will not be included in the analysis. If the day is missing, it will be imputed to the first day of the month.

Screening Disease History - MRI

- Number of Gd-enhancing T1 lesions at Screening as continuous and in categories (0,1,2,3, ≥ 4) at Screening
- Number of T2 lesions at Screening

Week 8 MRI – Baseline reset MRI

- Number of Gd-enhancing T1 lesions at Baseline reset as continuous and in categories (0,1,2,3, ≥ 4)

Ocrelizumab—F. Hoffmann-La Roche Ltd

15/Statistical Analysis Plan MA30005

- Volume of T2 lesions at Baseline reset
- Normalized brain volume at Baseline reset

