3. Check if the first EDSS assessment at a visit (unscheduled or scheduled) on or after the onset date of the relapse is increased by ≥ 0.5 steps from the previous EDSS; or selected FSS domains relevant to the relapse event (pyramidal, ambulation, cerebellar, brainstem, sensory, or converted visual) are increased by ≥ 2 points on one domain or ≥ 1 point on two or more domains. When deriving this step do the following:
 - Take the last EDSS/FSS score before each clinical relapse onset date
 - Take the first EDSS/FSS score on or after each clinical relapse onset date
 - Calculate the difference between the two scores
 - Select clinical relapses where there is an increase of ≥ 0.5 in EDSS or ≥ 2 on one appropriate FSS domain or ≥ 1 on two or more appropriate FSS domains
4. For each relapse that satisfies the 3 criteria above, check if the following relapses are within 30 days (i.e., the onset dates are ≤ 30 days apart). If they are within 30 days, then the later relapses are not PDR.

24-Week Confirmed Disability Progression (CDP) definition

Disability Progression as measured by EDSS is defined a ≥ 1 -point increase in EDSS score from a baseline EDSS score of 0.0–5.5 inclusive, and a 0.5-increase from a baseline EDSS score higher than 5.5. Because of the variability of EDSS, a single measurement at the baseline visit might not provide a sufficiently reliable baseline EDSS. Therefore, using an average score from two separate measurements may improve the reliability of baseline EDSS and the reliability of confirmed disability progression seen in the study. In the analysis of CDP, baseline EDSS is defined as the average of the EDSS scores at the screening and baseline visits (of note, any baseline visits occurring after the first dosing date will be disregarded in the computation of the baseline EDSS score), without rounding. If one of the EDSS scores from the screening or baseline visit was missing, the other was used for baseline EDSS.

Initial progression can happen at any scheduled or unscheduled visit during the 96-week treatment period.

An initial disability progression becomes confirmed if the following conditions are met:

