1. A sustained change in EDSS for a minimum of 24 weeks (-2 weeks) from the initial progression event i.e. the change in EDSS must be sustained at all available (scheduled or unscheduled) visits for a minimum of 24 weeks ($\geq 168-14$ days= 154 days) after initial progression. An “Early Discontinuation” visit can be used as a confirmation visit if it falls into the visit window (defined in the protocol) of any scheduled visit. The EDSS assessments (if any) between the initial disability progression and the confirmation of disability progression should be at least as high as the minimum change required for progression.
2. Scheduled visits within 30 days after the onset of a clinical relapse that meets conditions 1, 2 and 3 of a protocol-defined relapse definition cannot be used for confirmation of disability progression. The confirmation of the disability progression must then be based on the EDSS assessment at the next scheduled visit (which is not within 30 days of a protocol defined relapse).
3. If a patient has a missing assessment at the scheduled visit taking place at 24 weeks (≥ 154 days) after an initial progression, the confirmation of the disability progression must be based on the assessment at the next scheduled visit.

For the patients who have the initial progression at week 96 and roll over to the long term extension of Ocrelizumab study, a confirmation EDSS assessment will be collected in the long term extension (Liberto) study.

Patients who complete the treatment period without confirmed progression of disease will be censored at the date of their last EDSS assessment during the treatment period. Patients with an initial assessment of disease progression who subsequently discontinue

from the study without further assessments will not be considered to have confirmed disease progression, if the discontinuation reason is not lack of efficacy or death. Patients who discontinue from the study due to lack of efficacy or death without confirmed progression of disease will be imputed as having an event (i.e., CDP) at the time of discontinuation.

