4.4.2.4 Proportion of patients who have CDI

This endpoint will be analyzed on the ITT population.

For patients with a baseline EDSS score ≥ 2 , disability improvement is defined as a reduction in EDSS score ≥ 1.0 compared to baseline EDSS score. The same approach to data derivation of CDP will be used for the derivation of CDI, in particular the confirmation of the disability improvement at 24 weeks. For patients with baseline EDSS score < 2 , CDI will not be defined.

The proportion of patients who, over a 96-week period, have CDI will be presented along with a two-sided 95% Clopper-Pearson exact confidence interval.

Additionally, for patients with a baseline EDSS score ≥ 2 , the time to CDI will be defined as the number of days from baseline to CDI. The Kaplan–Meier method will be used to estimate the survival function for the time to CDI. Kaplan-Meier rates and Greenwood 95% CI using log-log transformation will be presented at 24 weeks, 48 weeks and 96 weeks. Kaplan-Meier plots will be produced.

4.4.2.5 Annualized rate of protocol-defined relapses at Week 96

This endpoint will be summarized for the ITT population.

The unadjusted annualized protocol-defined relapse rate will be defined as the total number of protocol-defined relapses for all patients divided by the total years of drug exposure (defined as the length of treatment period).

In addition, the adjusted annualized relapse rate will be estimated using a negative binomial model, adjusting for:

- Duration since MS Symptom Onset (≤ 3 years, >3 and ≤ 5 years, >5 years and ≤ 10 years, >10 years),
- presence of T1 Gd-enhanced lesions at Screening (Yes/No),
- presence of relapses prior screening as per CRF (Yes/No)
- number of previous DMTs (1, >1)

and including the log-transformed years of drug exposure time (in years) as an “offset” variable. The adjusted rates along with the two-sided 95% confidence interval will be presented.

Sample SAS code can be found below (SAS code is regarded as “draft” until fully validated at the analysis stage):

```
proc genmod data=ARR;
  class [covariates];
  model N_PDR = [covariates]/offset=EXPLOG link=log dist=negbin type3;
  estimate “Annualized rate” intercept 1 DISDUR xx xx T2VOL <mean value >
T1GD xx xx RELAPSE xx xx PDMT xx xx/ exp cl;
  ods output ParameterEstimates=est;
run;
```

As sensitivity analyses, the analyses specified above will be repeated on the annualized rate of clinical relapses at Week 96 (see section 4.4.4).

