4.4.5 Subgroup Analyses

The primary and the secondary efficacy endpoints will be summarized by the following subgroups, provided that they include at least 50 patients:

- Last DMT prior to study enrolment
 - Interferons (Interferon β 1a, Interferon β 1b, Peg Interferon β 1a)
 - Glatiramer acetate
 - Teriflunomide
 - Fingolimod
 - Dimethyl fumarate
 - Natalizumab
- Age (\leq 40 years, $>$ 40 years)
- Disease severity at inclusion and in disease history:
 - EDSS at baseline ($<$ 2.5, \geq 2.5)
 - Number of relapses over the year prior to inclusion (\leq 1, $>$ 1)
 - MRI at Week 8: presence of T1 Gd+ (Yes/No)
 - time between the qualifying disease activity event (last relapse prior to study) while on last DMT and 1st dose of ocrelizumab ($<$ 6 months, \geq 6 months)

In addition, changes in EDSS and ARR at week 96 will be summarized separately for patients with and without NEDA upto week 96. ARR will be only be repeated on the patients without NEDA up to week 96.

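### The SAP sets no relapse-related limit on the baseline EDSS, so recovery from a pre-baseline relapse can be counted as confirmed disability improvement

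*Protocol*

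**What the plan says.** - **Entry.** The Protocol Synopsis and 4.1.1 list "One or more clinically reported relapse(s" as one of three alternative qualifying events. Where treatment with the DMT has lasted over 12 months, a further condition applies: "at least one of the above events must have occurred within the last 12 months of treatment with this DMT". That limits how old the event may be, not how recent. No entry criterion asks for neurological stability before screening or Day 1. The nearest safeguard is an exclusion: "Systemic corticosteroid therapy within 4 weeks prior to screening".
- **Confirming progression.** In the 24-week CDP definition of SAP 4.4.1, condition 2 concerns "Scheduled visits within 30 days after the onset of a clinical relapse". If the relapse meets conditions 1 to 3 of the protocol-defined relapse derivation, such a visit cannot confirm progression.
- **Baseline.** For CDP, "baseline EDSS is defined as the average of the EDSS scores at the screening and baseline visits", without rounding. A baseline visit after first dosing is ignored, and a missing score is replaced by the other one. Relapse timing is not mentioned.
- **Improvement.** For patients with a baseline EDSS of at least 2, SAP 4.4.2.4 counts a fall of at least 1.0 "compared to baseline EDSS score. The same approach to data derivation of CDP will be used for the derivation of CDI". SAP 4.4.2.3 (EDSS change) gives no baseline definition of its own.
- **Relapse timing.** SAP 4.3 tabulates "Duration since last onset of MS relapse prior to enrollment and its category", with 3 months or less as the first category. SAP 4.4.5 has a subgroup on "time between the qualifying disease activity event (last relapse prior to study) while on last DMT and 1st dose of ocrelizumab", split at 6 months.
- **Sensitivity analyses.** None of analyses A to E in SAP 4.4.4 changes the EDSS baseline.

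**The concern.** The SAP guards against a temporary relapse deficit being confirmed as progression. It has no matching guard against the same kind of deficit raising the reference score. If a patient enters during recovery, the return to the usual level reads as improvement, and a single-arm trial has no comparator in which spontaneous recovery would also appear. CDI and mean EDSS change are the outcomes most exposed. SAP 4.3 itself expects some patients to have relapsed within 3 months of baseline.

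**Working it through.** **1. The plan's own precision figure.** The exact Clopper-Pearson interval for 225/750 is 26.74% to 33.42%, half-width 3.34 points. This matches the stated 26.7% to 33.4%. For 375/750 the half-width is 3.64. These figures serve only as a yardstick below.

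**2. The SAP rules applied to one patient.** Let E be the stable EDSS, and let s and b be the excess at the screening and baseline visits due to a relapse. The baseline shift is m = (s + b)/2. Full recovery counts as improvement if m ≥ 1.0 and E + m ≥ 2. CDP then needs a true worsening of 1.0 + m from the stable level.

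| Case | s | b | m | Full recovery reaches CDI threshold? | True worsening needed for CDP |
|---|---|---|---|---|---|
| Both raised equally | 1.0 | 1.0 | 1.0 | Yes | 2.0 |
| Partly recovered by baseline | 1.5 | 0.5 | 1.0 | Yes | 2.0 |
| Relapse between the two visits | 0 | 1.5 | 0.75 | No | 1.75 |
| Same, larger rise | 0 | 2.0 | 1.0 | Yes | 2.0 |

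Averaging gives no protection when both scores follow the same relapse. It halves the shift when only the baseline visit is affected. In that case a deficit that does not recover also counts towards CDP: with s = 0 and b = 1.5, the patient already sits 1.5 - 0.75 = 0.75 above the averaged baseline.

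**3. Timing.** Screening is 1 to 4 weeks before baseline (Protocol Appendix 1). For a relapse treated with steroids before screening, the last dose must be about 28 days or more before screening, hence 28 + 7 = 35 days or more before baseline. An EDSS within 30 days of relapse onset therefore comes mainly from relapses not treated with steroids, or from relapses starting during screening. Recovery lasting beyond 30 days is still accepted.

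**4. Size, under assumptions.** None of these inputs is in the documents. A relapse raises EDSS by 0.5, 1.0 or 1.5 in 30%, 50% and 20% of affected patients. Of these, 60% recover fully by Week 24. Rating error has SD 0.35, 8% truly progress, confirmation needs two consecutive visits, and the drug has no effect on disability. CDI among patients with baseline EDSS of at least 2:

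| Share with affected baseline | Both scores raised | Only baseline visit raised |
|---|---|---|
| 0% | about 1.3% | about 1.3% |
| 5% | about 3-4% | 1.7-1.9% |
| 10% | about 4-6% | 2.2-2.5% |
| 20% | about 8-10% | 3.2-3.5% |

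The ranges reflect choices the assumptions leave open, such as the distribution of stable EDSS. A cruder bound is excess CDI = share affected × probability of a later fall of at least 1.0. It runs from 5% × 25% = 1.25 points to 20% × 50% = 10 points. For comparison, the exact half-width for 40/400 is 3.1 points.

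**5. CDP and NEDA.** In affected patients, detected CDP falls from about 5.4% to about 2.3% when both scores are raised. When only the baseline visit is raised, it rises from about 4-5% to about 8-9%. In the first case, with 10% to 20% affected, the change in overall CDP is 3.1 × 0.10 = 0.3 to 3.1 × 0.20 = 0.6 points. That is before allowing for overlap with relapse and MRI events, and against a NEDA half-width of 3.3 points.

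**The case against.** The case for leaving the SAP alone has several parts.

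- **Condition 2 is narrower than it looks.** It covers only relapses meeting conditions 1 to 3, and condition 3 needs an EDSS or functional-system rise from the last score before onset. A relapse before screening has no earlier study score, so the condition cannot simply be carried over to baseline. A reader might infer that the SAP already contains the needed rule; it does not. This stands, and any baseline rule has to be written as new.
- **The steroid exclusion and the averaging remove much of the 30-day problem.** This stands for steroid-treated relapses and for those starting between the two visits. It does not cover untreated relapses before screening or slow recovery.
- **The plan already handles relapse history.** The EDSS model adjusts for baseline EDSS and enrolment reason, and subgroups use relapse count and the 6-month split. But enrolment reason says whether a relapse qualified the patient, not when it occurred. CDI has no adjustment. Six months is too wide to isolate recovery, and the subgroup wording can be read as leaving out a relapse after the last DMT was stopped.
- **CDI is one secondary endpoint in a descriptive study, and the affected share is unknown.** True. This limits the weight of the point, not its validity.

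**Conclusion.** The gap is real. Nothing in the entry criteria, the baseline definition, the subgroups or the sensitivity analyses separates recovery from a pre-baseline relapse from improvement on treatment. The documents support saying that such recovery can be counted as CDI, mainly when both pre-dose scores follow the same relapse.

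Two stronger readings are not supported. A reader might infer that most or all reported CDI would be relapse recovery; the affected share is not given, and the 8-10% figure needs 20% of patients affected with both scores raised. A reader might also infer that NEDA is biased upward. The CDP effect goes in opposite directions in the two cases, and its contribution to NEDA is a fraction of a point under the assumptions used.

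The excess in CDI is about 3 to 5 points at 10% affected with both scores raised (4-6% less 1.3%), comparable to sampling error. It is about 1 point if only the baseline visit is raised. This is worth a cheap sensitivity analysis. It is not a flaw in the primary result.

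**What to change.** In SAP 4.4.2.3, 4.4.2.4 and 4.4.2.7, and in the list in 4.4.4:

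1. Repeat EDSS change, CDI and CDP without patients whose last relapse began 3 months or less before the baseline visit, using the SAP 4.3 category. Include any relapse starting between screening and Day 1, and check that its onset date is captured, since the schedule of assessments starts recording potential relapses only at the baseline visit.
2. Flag patients with a screening or baseline EDSS scored within 30 days after a reported relapse onset. As a further sensitivity analysis, use the unaffected score alone where one exists. State this as a new rule for reported clinical relapses, not as an extension of condition 2.
3. Flag patients with partial relapse dates. SAP 4.3 sets a missing day to the first of the month, which can move a relapse out of either window, and it drops dates with only a year.

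The primary derivations, eligibility and visits stay as they are. The cost is one extra table per EDSS endpoint, some loss of precision from the excluded patients, loss of averaging for those analysed on one score, and a CDI rate that may look slightly less favourable.
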